### 5.6 Total Expected Duration of the Clinical Registry

Sites will follow enrolled subjects who receive physiologic pacing therapy for 6 months. The total expected duration of the registry is approximately 4 years, including enrollment, implant procedure, follow-up visits, and registry closure.

### 5.7 Expected Duration of Each Subject's Participation

The total expected duration of each subject's participation in the registry is approximately 6 months post implant of the device.

### 5.8 Number of Subjects Required for Inclusion in the Clinical Registry

The Physiologic Pacing Registry will have no formal power analysis and sample size calculation; the registry needs to enroll enough subjects from a comprehensive patient population to characterize the workflow associated with physiologic pacing device implants and to quantify the clinical utility of mapping physiologic pacing structures prior to device implants based on sites' routine care using the EnSite Cardiac Mapping System. The data from this registry will also be used to help inform Abbott's future product and clinical data development efforts and therefore must contain information from a wide variety of sites and subjects. [REDACTED]

### 5.9 Estimated Time Needed to Select Required Number of Subjects

[REDACTED]

## Physiologic Pacing Registry Clinical Plan

### 6.0 TREATMENT AND EVALUATION OF ENDPOINTS

#### 6.1 Baseline Clinical Assessments

Patients will undergo screening evaluations as outlined by the inclusion/exclusion criteria. The Principal Investigator (PI) or delegated research personnel are responsible for screening all potential patients to determine eligibility for the registry. All patients will complete a Baseline visit within 60 days prior to implant. During this visit, eligible patients will sign an EC/IRB-approved Informed Consent form. Once informed consent has been obtained, sites will collect the following data at the Baseline visit:

- Subject demographics
- Subject medical history
- Physical examination
- Cardiovascular history
- Indications for device implant
- LVEF, LVEDV, LVESV (if available)
- Tricuspid valve regurgitation and Mitral valve regurgitation severity by echo (if available)
- Intrinsic QRS duration using 12-lead ECG
- PR interval using 12-lead ECG
- Baseline conduction pattern using 12-lead ECG
- NYHA Classification

Sites must complete and submit the associated Baseline Visit Case Report Forms (CRFs) to Abbott using the electronic data capture (EDC) system.

#### 6.2 Implant Procedure

Investigators should follow their standard implant technique and workflow for physiologic pacing procedures and the associated devices indications for use. The decision to provide physiologic pacing therapy and selection of devices for implant are at the discretion of the implanting physician. Only subjects scheduled to receive an Abbott device may be enrolled to ensure proper device data collection for future software and other physiologic pacing product development; however, the investigator may use any market-approved lead and associated implant tools. If part of their routine clinical practice in physiologic pacing implants, physicians may create a 3-dimensional map of cardiac structures using any diagnostic mapping catheter with the EnSite Cardiac Mapping System.

Sites will collect the following data during the implant procedure:

- Fluoroscopy time and radiation dose
- Overall procedure time: skin-to-skin
- Implant procedure time: vascular access to lead fixation
- All Implant tools used
- Implant-related workflow
- Final implanted hardware

## Physiologic Pacing Registry Clinical Plan

- Final post-procedure device programming
- Procedure- and device-related adverse events and device deficiencies
- Implant success
- All types of physiologic pacing capture observed such as selective and non-selective
- Physiologic pacing capture and sensing thresholds
- Pacing output necessary to correct bundle branch block using 12-lead ECG (if applicable)
- QRS duration for all types of physiologic pacing captures observed using 12-lead ECG
- For His placement only: Measured H wave using device IEGM
- Measured R wave using device IEGMs through lead implanted for physiologic pacing

Investigators will program the implanted device based on their discretion. Sites must download the device session records and submit to Abbott using the EDC system. Sites must also submit a copy of the subject's physiologic pacing 12-lead ECG in digital format (if available). Sites must complete and submit the associated Implant visit CRFs to Abbott using the EDC system.

### 6.2.1 Unsuccessful Implants and Device Explants

Sites will follow subjects who have an unsuccessful implant of the lead implanted for physiologic pacing for a period of 30 days for procedure-related adverse events and then withdraw the subject from the registry, unless the physiologic pacing lead implant will be re-attempted. Sites should submit all available data for the attempted implant through what was completed during the procedure.

Sites will follow subjects who have their device or lead implanted for physiologic pacing explanted for a period of 30 days for procedure-related adverse events, and then withdraw the subject from the registry.

Sites will withdraw subjects from the registry if a lead implant for physiologic pacing was not attempted – no data collection at implant or following implant is required.

All explanted Abbott devices and Abbott leads should be returned to Abbott to the address below:

Sites must complete and submit a Product Out of Service CRF for any explanted devices to Abbott using the EDC system. After 30 days, if the investigator will not re-attempt implant of a lead for physiologic pacing, sites must complete and submit a Withdrawal CRF and Adverse Event CRF (if applicable) to Abbott using the EDC system.

The physician may re-attempt to implant a lead for physiologic pacing and/or Abbott device at their discretion within 30 days of the initial attempted implant. If the physician chooses to re-attempt the implant, site must complete and submit the associated Implant visit CRFs, an Adverse Event CRF (if applicable) and a Product Out of Service CRF (if applicable) to Abbott using the EDC system.

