
Another example of physiologic pacing is direct stimulation of the left bundle branch (left bundle branch pacing – LBBP). Indirect stimulation of the left bundle branch was first demonstrated by El-Sherif et al in CRT-indicated patients by using HBP and increasing the pacing output, thereby correcting left bundle branch block (LBBB). Direct LBBP was first reported by Huang et al during implant of a pacemaker in a patient with heart failure and LBBB. In this case, HBP with a high pacing output did not correct the LBBB but advancing the tip of the pacing lead to a more distal position did correct the LBBB at a lower pacing output. This resulted in a normalized QRS duration with prolonged AV delay, indicating synchronous LBBP with intrinsic RV stimulation was achieved. Similar to the reported effects of HBP, this patient saw significant improvement in their LVEF and significant reduction in heart failure symptoms. Based on these results, Huang et al proposed LBBP by stimulating distal to the diseased region for patients with heart failure and LBBB. Several subsequent studies have shown LBBP to be a safe and feasible pacing method not only for this patient population but also for patients with bradycardia. Similar to HBP, LBBP capture can be either selective or non-selective. Confirmation of LBB capture is typically verified by QRS morphology changes from LBB pacing, identification of the LBB potential recorded from the pacing lead, selective capture with specific ECG changes and EGM component, and evaluation of the time from pacing stimulus to LV activation. Other methods of activating the left bundle branch through indirect stimulation are emerging and may be assessed through this registry as well.

One major goal of physiologic pacing is to provide a consistent reduction in QRS duration. Physiologic pacing provides an opportunity to ensure the normalization of the QRS; however, many technical challenges remain, including: lead delivery, accurate His-Purkinje capture (selective vs. non-selective), and maintenance of stable pacing thresholds over time. The data collected from this registry will offer further evidence on the utility of physiologic pacing implants and currently available tools, as well as the potential advantages of enhanced localization of physiologic pacing structures using a 3-dimensional mapping system.

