### 3.1 Overall Flow of the Clinical Registry and Follow-up Schedule

The Physiologic Pacing Registry will evaluate subjects at baseline (before implant, Figure 1), implant, and at 1 month and 6 months post-implant. If part of their routine clinical practice in physiologic pacing implants, physicians may create a 3-dimensional map of cardiac structures utilizing the EnSite Cardiac Mapping System prior to implanting an Abbott device with any market available lead and associated implant tools. Only patients scheduled to receive an Abbott device may be enrolled to ensure proper device data collection for future software and other physiologic pacing product development.

Note: The site must receive approval from the Sponsor and EC/IRB prior to beginning registry enrollment. A patient is considered enrolled once the informed consent form has been signed (Figure 1).

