### 4.0 ENDPOINTS

#### 4.1 Registry Outcome Measures

The Physiologic Pacing Registry will collect data on the following measures as recommended by the His Bundle Pacing Collaborative Working group to characterize the workflow associated with physiologic pacing device implants and follow-up, and to quantify the clinical utility of mapping the cardiac structures prior to physiologic pacing device implants according to sites' routine care. Implant and follow-up characteristics will be compared with and without utilizing the EnSite Cardiac Mapping System during device implants.

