#### 7.3 Adverse Event, Device Deficiency, and Complaint Reporting

##### 7.3.1 Adverse Event Reporting

###### General Adverse Event Reporting

Safety surveillance and reporting starts as soon as the patient has an attempted implant in the registry. An attempted implant is defined as insertion of the physiologic pacing lead into vasculature. Safety surveillance and reporting will continue until the last follow-up visit has been performed, the subject is deceased, the subject concludes

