2.7 Subgroups for Analysis

Major implant characteristics will be summarized by subgroups, which include but are not limited to the following:

- Ensite Mapping system used to identify His signal [REDACTED]
- Physiologic pacing mode [REDACTED]

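### A procedure stopped after EnSite mapping but before lead insertion needs no implant data, so the comparison with and without mapping can be biased

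*Protocol*

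**What the plan says.** Protocol section 6.2.1 treats two kinds of subject differently.

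- **Lead attempted, implant failed.** The subject is followed for 30 days and then withdrawn unless a re-attempt is planned. The procedure data are kept: "Sites should submit all available data for the attempted implant through what was completed during the procedure".
- **Lead not attempted.** "Sites will withdraw subjects from the registry if a lead implant for physiologic pacing was not attempted – no data collection at implant". The rest of the sentence covers data after the implant and makes clear that collection is not required, rather than forbidden.

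The only visible definition of an attempt is in the safety section, 7.3.1: "An attempted implant is defined as insertion of the physiologic pacing lead into vasculature". Safety surveillance starts at that same moment.

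Mapping comes before it. Section 3.1 says that, where this is routine, "physicians may create a 3-dimensional map of cardiac structures utilizing the EnSite Cardiac Mapping System prior to implanting an Abbott device". Section 6.2 names the tool: "physicians may create a 3-dimensional map of cardiac structures using any diagnostic mapping catheter with the EnSite Cardiac Mapping System". In the schedule of events (Table 3), mapping is an optional item of the implant visit.

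The comparison is part of the stated objective. Section 4.1 says: "Implant and follow-up characteristics will be compared with and without utilizing the EnSite Cardiac Mapping System during device implants". SAP section 2.7 carries it as a subgroup summary of major implant characteristics under the label "Ensite Mapping system used to identify His signal". SAP section 3.3 lists subjects who did not go on to a physiologic lead among the early-termination reasons, with no visible split by mapping.

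**The concern.** Mapping with a diagnostic catheter is not an attempt under 7.3.1. If the operator maps and then stops before a physiologic lead goes in, 6.2.1 asks for no implant form. Because mapping is itself recorded at the implant visit, even the fact that the subject was mapped need not be captured. The procedure time, fluoroscopy time and dose already spent, and the reason for stopping, are lost with it.

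The registry sets out to quantify the clinical utility of mapping, and implant success, procedure time, fluoroscopy and adverse events are among the listed implant characteristics. Mapping adds an invasive step before the line at which data become mandatory. If procedures end at that step, they leave the mapped group's results. A complication of the mapping catheter that ends the procedure also falls outside the required safety period, and such a complication can arise only in mapped subjects.

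**Working it through.** **Is there a figure to reproduce?** No. SAP section 2.4 states that there is no hypothesis test and no formal sample size calculation. The documents give no rate of stopping before lead insertion, and the definition beside implant success in the SAP is redacted. Every rate below is an assumption.

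**What must be recorded, by where the procedure stops**

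| Procedure stops | Mapped | Unmapped |
|---|---|---|
| Before lead insertion | Implant data not required; safety period not begun | Same |
| After lead insertion, implant fails | Procedure data submitted; 30-day follow-up | Same |

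The rule is identical in the two columns. A bias arises only if the share stopping before lead insertion differs between the groups.

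**Formula.** Let p be the true success rate per procedure started, equal in both groups. Let a be the share of procedures started that stop before lead insertion. If those are dropped, the observed success rate is p/(1 − a). The spurious difference is p/(1 − a_mapped) − p/(1 − a_unmapped).

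**Results**

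| p | a mapped | a unmapped | Mapped appears | Unmapped appears | Difference (points) |
|---|---|---|---|---|---|
| 80% | 2% | 0% | 0.80/0.98 = 81.6% | 80.0% | +1.6 |
| 80% | 5% | 0% | 0.80/0.95 = 84.2% | 80.0% | +4.2 |
| 80% | 10% | 0% | 0.80/0.90 = 88.9% | 80.0% | +8.9 |
| 80% | 5% | 5% | 84.2% | 84.2% | 0 |
| 80% | 2% | 5% | 81.6% | 84.2% | −2.6 |
| 67% | 5% | 0% | 0.67/0.95 = 70.5% | 67.0% | +3.5 |
| 90% | 5% | 0% | 0.90/0.95 = 94.7% | 90.0% | +4.7 |

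**Scale.** SAP section 1.3 plans up to 1,000 subjects. Assume 500 mapped and 500 unmapped procedures started, p = 80%, and 5% against 0% stopped early. Then 25 mapped procedures drop out, leaving 400/475 = 84.2% against 400/500 = 80.0%. The 95% half-width of the difference is 1.96 × √(0.842 × 0.158/475 + 0.80 × 0.20/500) = 4.8 points. The spurious 4.2 points is close to the whole sampling uncertainty.

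**With every started procedure in the denominator**, both groups show p, and the spurious difference is 0 whatever the stopping rates.

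**The case against.** The strongest reply is that 6.2.1 does not mention mapping. An unmapped procedure stopped before lead insertion is dropped too, and a mapped one that fails after insertion is counted. That stands, and it is why the direction is conditional.

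A reader might infer that the plan is built to favour EnSite, because unmapped operators search for the target with the pacing lead and so fail only after the attempt line. The documents do not support this. The nearest text, in section 1.1.1, mentions "identification of the LBB potential recorded from the pacing lead" as one way to confirm left bundle branch capture; it does not say how unmapped operators find a target. The summary in Appendix IV allows an electrophysiology study, a map, or both, so an unmapped procedure could also end before a lead goes in.

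A reader might also infer that these subjects vanish. They do not: they remain in the Enrollment population (SAP section 2.1.1) and in the early-termination summary (SAP section 3.3), and sites may submit data voluntarily. Because mapping follows site routine, terminations by site might support a rough worst-case bound. None of this gives the individual mapping status needed to place a subject in a group, and SAP section 2.8 excludes missing data.

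The redacted text may define implant success and its denominator, and it is not criticised here. No definition can restore data that sites were not required to collect.

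On safety, Table 3 lists adverse events, where applicable, at baseline and implant. Section 7.3.1 nevertheless sets the start of reporting at lead insertion.

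Finally, the comparison is descriptive and non-randomized. No type I error is affected, but the estimates are what the registry will report.

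**Conclusion.** The gap is real and follows from reading 6.2.1 with 7.3.1: a procedure stopped after mapping and before lead insertion leaves no required implant data, no mapping status and no required safety record. The comparison with and without EnSite can therefore be biased. The sign for implant success depends on which group has more procedures stopped before lead insertion. It favours mapping if that group is the mapped one, which is plausible because mapping adds a step there, but it is not established.

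At an assumed 80% true success and no unmapped losses, the spurious gain is 1.6 to 8.9 points for 2% to 10% of mapped procedures lost. It is zero at equal losses and reverses if unmapped losses are larger. These figures also assume a denominator of lead attempts, which the visible text does not fix. The point merits a change because later analysis could not fully repair the loss.

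**What to change.** 1. **Protocol 6.2.1.** Limit the exemption from implant data to subjects in whom no procedure was started, meaning no vascular access, electrophysiology study or mapping.
2. **Implant CRF.** For every procedure started, mapped or not, require the existing form with mapping use, overall procedure time, fluoroscopy time and dose, adverse events and, as an added field if absent, the reason for stopping. Time from vascular access to lead fixation is marked not applicable when no lead is fixed.
3. **Protocol 7.3.1.** Start safety reporting at the start of the procedure, and make the definition of an attempt explicit in 6.2.1 so that both sections use the same one.
4. **SAP 2.7 and 3.3.** Report implant success by mapping status over all procedures started as well as over lead attempts, and split the count of subjects without a lead attempt by mapping status.

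The same rule must apply to both groups; counting early stops as failures only where mapping was used would create the opposite bias.

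The cost is one form for each affected subject. In the illustration, 2% to 10% of 500 mapped procedures is 10 to 50 forms, plus any for unmapped procedures stopped early. The success rate over all procedures started may be slightly lower than the rate over lead attempts.

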## Physiologic Pacing Registry Clinical Plan

### 6.3 Follow-up Assessments at 1 and 6 Months

The schedule of follow-up visits is based on the date of the successful implant of a lead for physiologic pacing with Abbott device implant. Table 2 outlines the time window permitted for each of the registry visits.

**Table 2: Registry Time Interval Windows**

1 Month	6 Months
-14 days/+30 days	± 60 days

Sites will follow all subjects at 1 month and 6 months after the date of successful HBP lead and Abbott device implant.

During each follow-up visit, the following data will be collected:

- Follow-up related workflow
- Physiologic pacing capture and sensing thresholds
- For His placement only: Measured H wave using device IEGM
- Measured R wave using device IEGMs through lead implanted for physiologic pacing
- Presenting QRS duration and PR interval from 12-lead ECG
- QRS duration for all types of physiologic pacing captures observed from 12-lead ECG
- Incidence of increase in capture threshold of > 1V in leads implanted for physiologic or RV pacing leads
- Far-field atrial oversensing and ventricular oversensing and/or any interventions – including programming – required to address these issues
- NYHA Classification
- LVEF, LVEDV, LVESV (if available)
- Tricuspid and mitral regurgitation severity by echocardiogram (if available)
- Device estimated battery longevity via device session records
- Frequency/burden of detected atrial and ventricular arrhythmias via device session records
- Procedure and device-related adverse events and device deficiencies

Sites must download the device session records and submit to Abbott using the EDC system. Sites must also submit copies of the subject's physiologic pacing 12-lead ECGs in digital format (if available). Sites must complete and submit the associated Follow-up visit CRFs to Abbott using the EDC system.

Sponsor Representatives may provide support during the follow-up procedures for device-related data collection.

#### 6.3.1 Unscheduled Visits

An unscheduled visit is defined as a visit between two registry-required visits during which the clinical site performs a device interrogation and reprogramming. Sites should download device session records and 12-lead ECGs (if available) and submit to Abbott using the EDC system. Sites must complete and submit the associated Follow-up visit CRFs, and any other applicable CRFs to Abbott using the EDC system.

## Physiologic Pacing Registry Clinical Plan

### 6.3.2 Schedule of Events

**Table 3: Schedule of Events**

CIP Activity	Baseline (≤ 60 days prior to implant)	Implant	1-Month (-14/+30 days post successful implant)	6- Month (±60 days post successful implant)	Unscheduled
Informed Consent Process	X				
Demographics	X				
Physical Examination	X		X	X	X
Cardiovascular History	X				
Implant indication	X				
Medical History	X				
NYHA Class	X		X	X	X
Implant Data Collection (Section 6.2)		X			
System Information		X			
Device Interrogation		X	X	X	X
Device Programming		X	X	X	X
12-lead ECG	X	X*	X	X	X
For His placement only: Measured H wave using device IEGM		X	X	X	X
Measured R wave using device IEGMs through physiologic pacing lead		X	X	X	X
Electro-anatomical Mapping (optional)		(X)			
LVEF (if available)	X			X	
Follow-up Data Collection (Section 6.3)			X	X	
Device Session Records		X	X	X	X
Adverse Event	(X)	(X)	(X)	(X)	(X)
Device Deficiency		(X)	(X)	(X)	(X)
Deviation	(X)	(X)	(X)	(X)	(X)
Termination	(X)	(X)	(X)	(X)	(X)
Assessment for Hospitalization			X	X	X
Death	(X)	(X)	(X)	(X)	(X)
Product Out of Service			(X)	(X)	(X)

(X) if applicable; \*If available

## Physiologic Pacing Registry Clinical Plan

### 7.0 ADVERSE EVENTS

To comply with worldwide standards and guidelines on adverse event reporting, Abbott has adopted uniform and worldwide applicable standard definitions and reporting timelines to be used and adhered to by the investigators.

#### 7.1 Definition

##### 7.1.1 Adverse Event

An adverse event is any untoward medical occurrence, unintended disease or injury, or untoward clinical signs (including abnormal laboratory findings) in subjects, users or other persons, whether or not related to the medical device under investigation.

**Note:** This definition includes events related to the procedures involved.

